4. STUDY PLAN AND TIMING OF PROCEDURES

The Schedule of Assessments is presented in [Table 2](#). The Schedule of Assessments for telephone visits is presented in [Table 3](#).

Table 2 Schedule of Assessments - Physical visits at study sites

	Screening period	Treatment period ^a											Follow-up period	For details see CSP Section
	Enrolment	Randomisation	3	4	6	9	12	15	18	21	24	End of Study (EOS)	Safety Follow-up	
Visit Number	1	2	3	4	6	9	12	15	18	21	24	End of Study (EOS)	Safety Follow-up	
Day/Week/Month	-7 d	0 d	2 wk	4 wk	3 mo ^b	6 mo ^b	9 mo ^b	12 mo ^b	15 mo ^b	18 mo ^b	21 mo ^b	{12 to 24 mo}	14d after EOS	
Visit Window	-28 to -7 d	N/A	±3 d	±7 d	±7 d	±7 d	±7 d	±7 d	±7 d	±7 d	±7 d	±14 d	±5 d	
Signed and dated informed consent/assent	X													10.4
Inclusion/exclusion criteria	X	X ^a												3.1 and 3.2
Assign E-code via IXRS	X													3.3
Relevant SCD, medical and surgical history	X													4.1
SCD diagnosis (if needed)	X													4.1
Demographics ^c	X													4.1
Transcranial Doppler ^d	X													4.1
Ophthalmology examination (if not performed within previous 12 months) ^d	X													4.1
Randomisation via IXRS		X												3.3 and 3.5
BP and pulse rate	X	X	X	X	X	X	X	X	X	X	X	X	X	5.2.4
Weight and height	X	X ^e				X		X		X		X		5.2.4
Physical examination (complete/brief) ^f	X	X	X	X	X	X	X	X	X	X	X	X	X	5.2.2
12-Lead ECG	X					X						X	X	5.2.3
Malaria testing for symptomatic patients ^g	X													4.1
Virology screen (HIV, HBsAg, and HCV)	X													5.2.1

Table 2 Schedule of Assessments - Physical visits at study sites

	Screening period	Treatment period ^a											Follow-up period	For details see CSP Section
	Enrolment	Randomisation	3	4	6	9	12	15	18	21	24	End of Study (EOS)	Safety Follow-up	
Visit Number	1	2	3	4	6	9	12	15	18	21	24	End of Study (EOS)	Safety Follow-up	
Day/Week/Month	-7 d	0 d	2 wk	4 wk	3 mo ^b	6 mo ^b	9 mo ^b	12 mo ^b	15 mo ^b	18 mo ^b	21 mo ^b	{12 to 24 mo}	14d after EOS	
Visit Window	-28 to -7 d	N/A	±3 d	±7 d	±7 d	±7 d	±7 d	±7 d	±7 d	±7 d	±7 d	±14 d	±5 d	
Blood samples for haematology and clinical chemistry	X	X ^h	X	X		X		X		X		X	X	5.2.1
Blood samples for coagulation (INR, PT and APTT)	X													5.2.1
Urine pregnancy Test ⁱ	X	X	X	X	X	X	X	X	X	X	X	X	X	5.2.1
Urine for urinalysis (dipstick)	X	X ^h		X		X		X		X		X	X	5.2.1
Training and handout/collection of eDevice		X										X		
Review of eDevice device entries and reminder of use ^j			X	X	X	X	X	X	X	X	X	X		5.3.1

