7.2.1 Treatment during double-blind randomisation period

Randomisation to twice daily double-blind treatment with ticagrelor or placebo will occur at Visit 2 via the IXRS. Eligible patients will be randomly assigned to 1 of 2 treatment regimens, based on body weight at Visit 2:

- ≥ 12 to ≤ 24 kg body weight: 15 mg - 1 tablet of ticagrelor 15mg or 1 tablet of placebo to match ticagrelor 15 mg twice daily
- > 24 to ≤ 48 kg body weight: 30 mg - 2 tablets of ticagrelor 15mg or 2 tablets of placebo to match ticagrelor 15mg twice daily
- > 48 kg body weight: 45 mg - 3 tablets of ticagrelor 15mg or 3 tablets of placebo to match ticagrelor 15mg twice daily

At Visit 2, the first dose of IP will be administered at the clinic by site staff as soon as possible after randomisation and after all baseline assessments have been completed. Subsequent doses should be taken morning and evening, at approximately 12-hour intervals. Missed doses of ticagrelor or placebo blinded IP should not be compensated (ie, if a dose is missed the next regularly scheduled dose should be taken and should not be doubled).

The study drug will be administered orally either swallowed whole or dispersed in water, other suitable liquids or vehicles based on age and/or ability to swallow study drugs. Refer to handling instructions for further details.

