3.1.2 Baseline

Baseline is the last assessment collected (scheduled or unscheduled) prior to the first dose of study treatment, or last assessment collected prior to or at randomisation (Visit 2), for patients who are randomised but do not receive any study treatment. For in-clinic assessments with an assessment date equal to the first dose of study treatment, the assessment will be assumed to be pre-dose since all assessments are to be done prior to dispensing study treatment according to the protocol. For adverse events (AEs) and concomitant medications with start date equal to the first dose of study treatment, the event will be considered post-baseline.

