- Maximum on-treatment: Highest test result (scheduled or unscheduled value) observed within the period from date of first dose of study treatment up to and including date of last dose of study treatment + 7 days.
- Minimum on-treatment: Lowest test result (scheduled or unscheduled value) observed within the period from date of first dose of study treatment up to and including date of last dose of study treatment + 7 days.

In addition to the aforementioned assessments, treatment-emergent change from baseline in observed values (scheduled and unscheduled) will be identified as compared to the relevant laboratory references range, where treatment-emergent is defined as follows:

- Treatment-emergent = Regarded as treatment-emergent if the post-baseline assessment on-treatment is “worse” than baseline (refer to Section 3.1.7.1 for further details).
 - Increase: In the identification of treatment-emergent high values, change from baseline categories “normal” AND “low” will be considered.
 - Decrease: In the identification of treatment-emergent low values, change from baseline categories “normal” AND “high” will be considered.

For example: Patient 1

Alkaline Phosphatase	Baseline	Normal	
Alkaline Phosphatase	Visit 9	Normal	

Alkaline Phosphatase	Visit 15	High	Treatment-emergent high (increase)
----------------------	----------	------	------------------------------------

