3.4.9 Vital Signs

Vital signs (blood pressure and pulse rate) will be measured after 5 minutes rest as per schedule of assessments (refer to Table 2 of the latest version of the CSP). Weight and height assessments will be performed at the visits as shown in Table 2 of the latest version of the CSP.

Change from baseline in vital signs to each post-baseline assessment (scheduled and unscheduled) will be calculated as described in [Section 3.1.3](#).

Vital signs collected at any time during the study (scheduled and unscheduled) will be compared to the pre-defined abnormality assessment criteria reported in [Table 4](#) (refer to Vital Signs Pre-defined Abnormality Assessment Criteria). The assessment of pre-defined abnormalities for systolic blood pressure (SBP), diastolic blood pressure (DBP) and pulse rate will be based on the upper/lower limits as relevant given the patient’s age (years) at the time of the assessment and categorised as:

- Low: Below lower limit of the age-specific abnormality assessment criterion ($< LL$)
- Normal: Within the lower limit and upper limit of the age-specific abnormality assessment criterion, limits inclusive ($\geq LL$ to $\leq UL$)
- High: Greater than upper limit of the age-specific abnormality assessment criterion ($> UL$)

All observed values falling outside these criteria limits will be flagged.

Specifically, change from baseline to maximum/minimum values on-treatment (refer to [Section 3.1.7.1](#)), categorised as described above per abnormality assessment criteria, will be presented, where maximum and minimum vital signs results will be identified as:

- Maximum on-treatment: Highest vital signs result (scheduled or unscheduled value) observed within the period from date of first dose of double-blind randomised study treatment up to and including date of last dose of double-blind randomised study treatment + 7 days.
- Minimum on-treatment: Lowest vital signs result (scheduled or unscheduled value) observed within the period from date of first dose of double-blind randomised study treatment up to and including date of last dose of double-blind randomised study treatment + 7 days.

In addition to the aforementioned assessments, treatment-emergent change from baseline in observed vital signs values (scheduled and unscheduled) will be identified as compared to the relevant abnormality assessment criteria, where treatment-emergent is defined as follows:

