4.2.9.5 Laboratory Variables

With reference to the general principles and definitions detailed in Sections 2.1, 3.1 and 4.1.1, laboratory variables will be summarised using the safety analysis set, by actual treatment group. Relevant data will be presented in patient data listings.

For continuous variables, observed values and change from baseline will be summarised for each clinical chemistry, haematology, and urinalysis variable at each scheduled time point (per planned eCRF visit [number and name]). For categorical variables, shift tables will be presented for the change from baseline by actual treatment group.

Box plots of observed values and change from baseline will also be presented for each clinical chemistry, and haematology laboratory variable.

For each laboratory variable, a shift table will be produced presenting the baseline value classification according to laboratory reference range versus the minimum and maximum on-treatment value.

Descriptive statistics, summarising patients with at least one treatment-emergent change (high [increase]/low [decrease]) per laboratory variable, based on laboratory reference ranges, will be presented by actual treatment group (refer to Section 3.4.7). Where:

- n = Number of patients with at least one treatment-emergent change occurring on-treatment (patients with multiple occurrences on-treatment will only be counted once).
- % = Percentage of patients in the safety analysis set with at least one treatment-emergent change occurring on-treatment relative to the total number of patients in the safety analysis set, with a baseline and at least one post-baseline assessment on-treatment available.

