4.2.9.5.1 Liver Enzyme Elevations and Hy's Law

The following summaries will include the number (n) and percentage (%) of patients in the safety analysis set with at least one post-baseline liver function assessment available in the defined double-blind randomised treatment period and identified as on-treatment or off-treatment (refer to Section 3.1.7.1 and 3.1.7.2), who have:

- Elevated ALT, AST, and total bilirubin over the defined treatment period
 - ALT <3, ≥3× to <5×, ≥5× to <10×, ≥10× ULN
 - AST <3×, ≥3× to <5×, ≥5× to <10×, ≥10× ULN
 - Total bilirubin <2×, ≥2× ULN
 - ALT or AST <3×, ≥3× to <5×, ≥5× to <10×, ≥10× ULN

- ALT or AST $\geq 3 \times$ ULN and total bilirubin $\geq 2 \times$ ULN (Potential Hy's law): The onset date of ALT or AST elevation should be prior to or on the date of total bilirubin elevation.

To identify potential Hy's Law cases, a listing of patients in the safety analysis set who have ALT or AST $\geq 3 \times$ ULN and total bilirubin $\geq 2 \times$ ULN at any time during the study (ie, not necessarily at the same time) following first dose of double-blind randomised study treatment administration will be provided. This listing will include all assessments (scheduled and unscheduled) for this subset of patients over the entire study course. Dose level at the time of liver function assessments will also be presented.

A shift plot will also present maximum on-treatment (refer to Section 3.4.7) ALT observed value by maximum on-treatment total bilirubin observed value, expressed as multiples of ULN. A similar plot will be presented for maximum on-treatment AST observed value. Reference lines will be included at $2 \times$ ULN for total bilirubin and $3 \times$ ULN for ALT/AST.

Additionally, a figure presenting the individual liver biochemistry test results over time for patients with elevated ALT or AST, and elevated total bilirubin at any time following first dose of double-blind randomised study treatment administration will be provided. Results will be expressed as multiples of ULN.

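### The on-treatment maximum and minimum for laboratory tests and vital signs start on the date of first dose with no post-baseline condition, so a Visit 2 baseline record also counts as an on-treatment value

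*SAP*

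**What the plan says.** **Baseline.** SAP 3.1.2 takes the last assessment before first dose and adds a rule for same-day records: "For in-clinic assessments with an assessment date equal to the first dose of study treatment, the assessment will be assumed to be pre-dose".

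**On-treatment extremes.** SAP 3.4.7 defines the laboratory maximum as "Highest test result (scheduled or unscheduled value) observed within the period from date of first dose of study treatment" and the minimum as "Lowest test result (scheduled or unscheduled value) observed within the period from date of first dose of study treatment", both running to last dose plus 7 days. SAP 3.4.9 defines the vital-sign maximum as "Highest vital signs result (scheduled or unscheduled value) observed within the period from date of first dose of double-blind randomised study treatment", with a matching minimum. None of these definitions says post-dose or post-baseline.

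**Timing of Visit 2.** Protocol 7.2.1 states: "At Visit 2, the first dose of IP will be administered at the clinic by site staff as soon as possible after randomisation", once the baseline assessments are done. Protocol Table 2 schedules blood pressure, pulse, haematology and clinical chemistry at that visit.

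**Where the extremes are used.** The laboratory shift table (SAP 4.2.9.5) sets the baseline category "versus the minimum and maximum on-treatment value". SAP 4.2.9.7 does the same for systolic pressure, diastolic pressure and pulse. In SAP 4.2.9.5.1, "A shift plot will also present maximum on-treatment" ALT (and, in a second plot, AST) against maximum on-treatment total bilirubin, and cites Section 3.4.7 for the definition.

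**The concern.** A record that the SAP itself deems pre-dose falls inside a window labelled on-treatment. A programmer who follows the definition as written compares the baseline with a set that contains it. The extremes can then move in only one direction from baseline.

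Three other things follow:

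- A patient with no post-dose sample still receives an on-treatment maximum and minimum, both equal to baseline.
- Protocol exclusion criterion 9 tolerates bilirubin above 2 x ULN when the investigator attributes it to haemolysis. Such a pre-dose value can be the plotted maximum on-treatment bilirubin, against a 2 x ULN reference line, paired with an ALT peak from a later date.
- Handling depends on scheduling. Protocol 4.1 and Table 2 footnote h let Visit 1 results less than 10 days old replace the Visit 2 laboratory sample. For those children the laboratory baseline predates the window and is excluded; for the others it is included.

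**Working it through.** The plan gives no figure to reproduce. The check compares date windows; the arithmetic only indicates scale.

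**1. Overlap of the windows.** Let D be the date of first dose, which is the Visit 2 date.

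- Baseline rule (SAP 3.1.2): an in-clinic record dated D is pre-dose, so it is eligible as baseline and, if it is the last such record, is the baseline.
- Extreme rule (SAP 3.4.7, 3.4.9): any scheduled or unscheduled record dated from D to last dose + 7 days is eligible.

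A Visit 2 record dated D meets both. Writing b for baseline and x1 to xk for the k later on-treatment values, the plan's maximum is max(b, x1, ..., xk) ≥ b and its minimum is min(b, x1, ..., xk) ≤ b. With k = 0 both equal b.

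**2. From values to categories.** If the same upper limit applies throughout, b above the limit forces the maximum above it, so High-to-Normal cannot occur in the maximum table. The mirror argument removes Low-to-Normal from the minimum table. But SAP 3.4.7 and 3.4.9 use limits for age at the time of assessment, so exceptions exist. From SAP Table 4:

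- The systolic upper limit is 120 at 8 to <12 years and 125 at 12 to <14. A baseline of 121 at age 11 is High; a later 124 at age 12 is the maximum and is Normal.
- The pulse lower limit is 70 at 4 to <6 years and 65 at 6 to <8. A baseline of 68 at age 5 is Low; a later 66 at age 6 is the minimum and is Normal.

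**3. How often the baseline would be the extreme.** Assume no drug effect and exchangeable continuous values. The baseline is then the largest of k + 1 values with probability 1/(k + 1). The counts of k come from Protocol Table 2.

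| Data | Scheduled post-baseline visits | k | 1/(k + 1) |
|---|---|---|---|
| Haematology, chemistry | Visits 3, 4, 9, 15, 21, EOS | 6 | 14.3% |
| Blood pressure, pulse | Visits 3, 4, 6, 9, 12, 15, 18, 21, 24, EOS | 10 | 9.1% |
| Shortened follow-up | two values | 2 | 33.3% |

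**4. Illustrative reclassification.** Model: X_t = √ρ·S + √(1−ρ)·E_t, with S and E_t independent standard normal and one fixed upper limit c, so that a proportion p of values is High. The quantity is P(max of m post-baseline values ≤ c, given baseline > c). The values of p and ρ are assumptions; neither document gives them. Each range is over ρ = 0.6 to 0.8.

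| p | m = 1 | m = 4 | m = 6 |
|---|---|---|---|
| 20% | about 35–50% | 11–18% | 8–12% |
| 40% | 25–36% | 6–9% | 4–5% |

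Under this fixed-limit model the plan's rule gives 0% in every cell for patients with a Visit 2 baseline.

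The effect on the overall share of patients with a High maximum is smaller. With p = 5% and m = 6, including the baseline raises it from 26.4% to 30.2% at ρ = 0, from 18.6% to 20.3% at ρ = 0.5, and from 12.6% to 13.4% at ρ = 0.8.

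**5. Outputs that do not use these extremes.**

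- The treatment-emergent rule in SAP 3.4.7 and 3.4.9 requires a post-baseline assessment.
- The liver category summaries require at least one post-baseline assessment.
- The potential Hy's Law listing and the individual liver time-course figure are limited to elevations after first dose.
- By-visit summaries and box plots use scheduled visits.

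**The case against.** The strongest reply is that post-dose values were plainly intended. The definitions support a change from baseline to the extremes, and SAP 3.1.3 defines change using a post-baseline value. SAP 3.4.9 refers to SAP 3.1.7.1, where the on-treatment period begins at first dose and not at its date. Read together, these would exclude the Visit 2 record. This is a fair account of intent, and it is stronger for vital signs than for laboratory tests, where the sentence introducing the definitions lacks that cross-reference. It does not override an explicit definition that starts on a calendar date and omits a condition the same sections impose for treatment-emergent changes.

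A reader might also infer more than the documents support:

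- **That High-to-Normal and Low-to-Normal shifts are impossible for every child.** Limits depend on age at assessment, and follow-up can last 24 months, so the exceptions in step 2 can occur.
- **That the safety outputs cannot show improvement.** A fall from High can still appear in the minimum table and a rise from Low in the maximum table. By-visit values, changes from baseline and box plots show both directions.
- **That potential Hy's Law identification is contaminated.** Only the maximum-by-maximum plot takes the SAP 3.4.7 definition. The reclassification figures concern a single upper limit and say nothing about the 2 x ULN line.

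It is also true that the rule is the same in both arms, that SAP 4.2.9 plans no formal safety testing, and that with six later samples 88–96% of baseline-High patients would stay High under the assumptions used.

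**Conclusion.** The definitions are wrong as written, at minor severity. For patients whose baseline is dated on the first-dose day, a pre-dose record counts as on-treatment, so the maximum value is never below baseline and the minimum never above it. With unchanged limits this empties the High-to-Normal cell of the maximum table and the Low-to-Normal cell of the minimum table. A same-day baseline is the planned case for blood pressure and pulse and the usual one for haematology and chemistry. It does not arise where Visit 1 results stand in for the Visit 2 sample, or for coagulation, which is sampled at screening only.

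The damage is confined to the laboratory and vital-sign minimum/maximum shift tables and the ALT/AST-by-bilirubin plots, in both arms. The primary analysis is untouched. Shifts from Normal to abnormal are correctly shown where post-dose values exist. The distortion grows as the number of post-dose samples falls, which is relevant because SAP 3.1.4.1 records that the study stopped early. The percentages rest on assumed prevalence, correlation and a fixed limit; they show scale and are not estimates for this trial.

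**What to change.** In SAP 3.4.7 and 3.4.9, define the on-treatment maximum and minimum over post-baseline records only: those after the baseline assessment, up to and including last dose + 7 days. In SAP 4.2.9.5, 4.2.9.5.1 and 4.2.9.7, limit the minimum/maximum shift tables and the liver plots to patients with at least one such record. SAP 4.2.9.6 already applies this kind of denominator to the ECG shift table.

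The cost is one phrase in each of two definitions and a denominator statement for the affected outputs. No new data are needed, and children whose Visit 1 sample served as baseline are then handled like everyone else.

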1.3 Benefit/risk and ethical assessment

The aim with ticagrelor treatment in paediatric patients with SCD is to reduce the rate of VOCs, with an acceptable safety profile. Considering that the anticipated benefit would be mostly symptom reduction and that patients with SCD suffer from anaemia, the acceptance for bleedings will be low.

Episodes with VOCs are the most common cause for emergency room visits for children with SCD. The pain associated with VOC can be excruciating and have a significant impact on the child's life, and significantly disturbs routine activities such as food intake, sleep and school

activities during several days. The painful crises are repeatedly described as the most challenging symptom of their disease by patients with SCD. An ACS is a serious and potentially life-threatening condition that may lead to respiratory failure or multi organ failure, and is a common cause of death in SCD patients. Most cases of ACS require hospitalisation for >1 week (Vichinsky et al 2000). Besides the acute symptoms, the ischaemia during vaso-occlusion causes tissue damage that over time leads to impaired organ function (eg, renal failure) or complications such as bone necrosis, joint pain or cognitive impairment. Pharmacological treatments options to prevent VOC events in children are few and side effects can be dose-limiting (hydroxyurea). With previous studies of anti-platelet drugs suggesting potential to reduce VOCs (Cabannes et al 1984, Heeney et al 2016) and the high unmet need for new treatments, there is a clear value in continuing to investigate the role of anti-platelet therapies in the reduction of VOCs.

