3.2 Exclusion criteria

Patients should not enter the study if any of the following exclusion criteria are fulfilled:

1. History of transient ischaemic attack (TIA) or cerebrovascular accident (ischaemic or haemorrhagic), severe head trauma, intracranial haemorrhage, intracranial neoplasm, arteriovenous malformation, aneurysm, or proliferative retinopathy.
2. Findings on TCD: Current or previous values for time averaged mean of the maximum velocity (TAMMV) that are Conditional or Abnormal. Patients with Conditional TAMMV values or higher (≥ 153 cm/sec using TCD imaging technique [TCDi] which is corresponding to ≥ 170 cm/sec by the non-imaging technique). Both the middle cerebral artery and the internal carotid artery should be considered. Any other criteria that would locally be considered as TCD indications for chronic transfusion would also exclude the patient.
3. Active pathological bleeding or increased risk of bleeding complications according to Investigator
4. Haemoglobin < 6 g/dL from test performed at Screening (Visit 1)
5. Platelets $< 100 \times 10^9/L$ from test performed at Screening (Visit 1)
6. Undergoing treatment with chronic red blood cell transfusion therapy

7. Chronic use of NSAIDs defined as continuous intake >3 days per week that cannot be discontinued
8. Receiving chronic treatment with anticoagulants or antiplatelet drugs that cannot be discontinued
9. Moderate or severe hepatic impairment defined as laboratory values of alanine aminotransferase (ALT) >2 × upper limits of normal (ULN), total bilirubin >2 × ULN (unless judged by the Investigator to be caused by haemolysis), albumin <35 g/L (3.5 g/dL) and International normalised ratio (INR) >1.4, or symptoms of liver disease (eg, ascites) from test performed at Screening (Visit 1).
10. Renal failure requiring dialysis
11. Patient considered to be at risk of bradycardic events (eg, known sick sinus syndrome or second or third-degree atrioventricular block) unless already treated with a permanent pacemaker.
12. Concomitant oral or intravenous therapy with strong cytochrome P450 3A (CYP3A) inhibitors, CYP3A substrates with narrow therapeutic indices, or strong CYP3A inducers (see full list in [Appendix G](#)), which cannot be stopped at least 5 half-lives before randomisation.
13. Active untreated malaria. Patients with suspected malaria at Screening (Visit 1) will be tested.
14. Known hypersensitivity or contraindication to ticagrelor

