8.5.4 Analysis of the safety variables

Adverse events will be coded using the Medical Dictionary for Regulatory Activities (MedDRA). Number of patients with events and percentages will be tabulated by preferred term and system organ class. An event that occurred once or more times during the treatment period will contribute 1 observation to the numerator of the proportion. The denominator of the proportion will comprise all patients in the safety set. Adverse events will also be summarised by intensity/severity and separately, by causality/relatedness (as determined by the Investigator). Should a patient report the same preferred term/system organ class within multiple intensity/severity or causality/relatedness categories, the patient's worst occurrence (most severe/most related) will be tabulated. Serious AEs, AEs leading to discontinuation of IP, and commonly occurring AEs will be summarised in a generally similar manner. Adverse events, SAEs, AEs leading to death, and AEs leading to discontinuation of IP will be summarised for each treatment group as applicable.

Laboratory data will be summarised by presenting shift tables from baseline to end of study using normal ranges and by presenting summary statistics of observed and change from baseline values (means, medians, quartiles, ranges). The incidence of clinically notable laboratory abnormalities will be summarised.

Vital sign data will be summarised by presenting summary statistics of observed and change from baseline values. The incidence of clinically notable vital sign abnormalities will be summarised.

For summarising of bleeding event, the number and percent of patients who experience (1) at least 1 bleeding event; (2) at least 1 major bleeding event; (3) at least 1 major or clinically relevant non-major bleeding event; (4) at least 1 minor bleeding event, will be presented by treatment group. The total number of events will also be provided.

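### The treatment-emergent low flag cannot register worsening haemoglobin in patients already below the lower limit of normal at baseline, and no other planned table counts large falls without overt bleeding

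*SAP*

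**What the plan says.** SAP 3.4.7 sorts each laboratory value into low, normal or high against a reference range specific to age and, where relevant, sex. Its general definition of a treatment-emergent change is: "Regarded as treatment-emergent if the post-baseline assessment on-treatment is “worse” than baseline". Two bullets then make this operational. For high values: "In the identification of treatment-emergent high values, change from baseline categories “normal” AND “low” will be considered". For low values: "In the identification of treatment-emergent low values, change from baseline categories “normal” AND “high” will be considered".

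SAP 4.2.9.5 reports the number and percentage of patients with at least one such change. The percentage is taken "relative to the total number of patients in the safety analysis set, with a baseline and at least one post-baseline assessment on-treatment available".

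On the population, Protocol 1.3 notes that "patients with SCD suffer from anaemia, the acceptance for bleedings will be low". Exclusion criterion 4 in Protocol 3.2 bars only haemoglobin below 6 g/dL at screening.

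On reporting, Protocol 8.5.4 states: "The incidence of clinically notable laboratory abnormalities will be summarised". The SAP supplies numerical limits for vital signs (Appendix A) and for liver tests (4.2.9.5.1), but none for haemoglobin. SAP Table 3, which lists changes from the protocol, does not mention this.

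**The concern.** Haemoglobin is a main laboratory marker of blood loss, and the trial drug is an antiplatelet agent in children whom the protocol describes as anaemic and in whom it accepts little bleeding. The table that should show who worsened on treatment uses a rule under which a child who starts low cannot worsen. The same table gives full weight to a trivial fall across the limit. Because the children who cannot be flagged remain in the denominator, the percentage is also diluted.

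At stake is how readable one safety table is. A small figure in both arms could reflect the rule rather than the drug. The primary efficacy analysis is not affected.

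**Working it through.** The plan states no figure to reproduce, so the check applies the rule as written and then looks at what the other outputs would show.

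**1. The rule on example values.** Inputs: the low, normal and high categories and the treatment-emergent bullets of SAP 3.4.7. The documents give no haemoglobin LLN, so 105, 115 and 130 g/L were assumed in turn. The results were the same for all three.

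| Baseline to on-treatment Hb (g/L) | Fall (g/L) | Out-of-range flag | Treatment-emergent low |
|---|---|---|---|
| 80 to 60 | 20 | yes | no |
| 90 to 50 | 40 | yes | no |
| 60 to 40 | 20 | yes | no |
| LLN to LLN − 1 | 1 | yes | yes |
| LLN + 5 to LLN − 20 | 25 | yes | yes |

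So a 40 g/L fall from a low baseline is not treatment-emergent, and a 1 g/L fall across the limit is. This is at odds with the general definition in the same section, which asks only whether the value is worse than baseline.

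**2. The ceiling on the percentage.** Let s be the share of patients below LLN at baseline. Only the remaining 1 − s can ever be counted, while the denominator includes everyone with a baseline and an on-treatment value. The largest possible treatment-emergent low percentage is therefore 100 × (1 − s). The documents do not give s. With 182 patients planned at 1:1, there are 182 / 2 = 91 per arm.

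| Assumed s | Ceiling | Patients per arm who could be counted |
|---|---|---|
| 70% | 30% | 91 × 0.30 = 27.3 |
| 80% | 20% | 91 × 0.20 = 18.2 |
| 90% | 10% | 91 × 0.10 = 9.1 |
| 100% | 0% | 0 |

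**3. Where a fall from 90 to 50 g/L without overt bleeding would appear.**

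- Out-of-range flag (SAP 3.4.7): present, but it fires equally at 90 and at 50.
- Shift table to the on-treatment minimum (SAP 4.2.9.5): in the Low to Low cell, together with stable anaemia.
- Change-from-baseline summaries by visit: included if the sample was scheduled. SAP 3.1.8 keeps unscheduled results out of by-visit summaries, and Protocol Table 5 plans no blood at months 3, 9, 15 and 21. Unscheduled values do reach the minimum-value and treatment-emergent tables, which are the ones that show no change here.
- Bleeding tables: the 20 g/L criterion for major bleeding (SAP 3.4.4) applies only when there is clinically overt bleeding.
- Adverse events: Protocol 6.3.6 has deterioration in protocol-mandated tests reported only if it is serious or leads to stopping study drug. Associated signs or symptoms are reported in their own right.
- Transfusion tables (SAP 4.2.9.4): these count treatment given, not the fall.

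None of these gives a count of patients by arm with a large haemoglobin fall without overt bleeding.

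**The case against.** The strongest reply is that haemoglobin is reported in several other ways. Every out-of-range value is flagged. Summaries of change from baseline include the minimum, so the largest fall at each scheduled visit is visible by arm. Overt bleeding with a fall of at least 20 g/L is major bleeding and is tabulated. Transfusions are tabulated, and Protocol Appendix A names anaemia requiring transfusion as an example of an important medical event. The data monitoring committee sees unblinded individual data (Protocol 1.5.2). All of this stands. It narrows the gap to large falls without overt bleeding, associated symptoms, transfusion or seriousness, which remain uncounted by arm.

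A reader might go further and infer that such a fall would pass unflagged altogether. That is not so, because SAP 3.4.7 flags it as out of range; only the treatment-emergent label is withheld.

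A reader might also extend the point to bilirubin and Hy's Law, since exclusion criterion 9 in Protocol 3.2 includes "total bilirubin >2 × ULN (unless judged by the Investigator to be caused by haemolysis" and the potential Hy's Law row carries an order condition: "The onset date of ALT or AST elevation should be prior to or on the date of total bilirubin elevation". The documents largely answer this. SAP 4.2.9.5.1 tabulates bilirubin by multiples of the upper limit of normal (ULN) whatever the baseline, adds plots of maximum values, and lists patients meeting both criteria at any time after first dose without the order condition. What is left is that a rise from a baseline already at or above 2 × ULN stays in the same band, which does not justify a change here. Nor do the documents show the rule failing for platelets; entry requires a count of at least 100 × 10^9/L.

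**Conclusion.** The point holds for haemoglobin. For a patient below LLN at baseline, the treatment-emergent low flag cannot fire, and that patient still counts in the denominator. The SAP also sets no haemoglobin criterion for the notable-abnormality incidence promised in Protocol 8.5.4.

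The size depends on the share low at baseline. The protocol supports a high share in words but gives no figure. Under an assumed 80% to 100%, the ceiling is 20% to 0%.

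A reader might conclude that the table must read near zero in both arms. That does not follow: a ceiling of 10% or 20% leaves room for a visible figure, and the row also counts small falls across the limit. Nor can an assumed difference between arms simply be multiplied by the share at risk and called a maximum. That product is an expected value if large falls are unrelated to baseline category, which the documents do not establish.

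This is a cheap improvement to descriptive safety reporting.

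**What to change.** In SAP 3.4.7 and 4.2.9.5:

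- Add the number and percentage of patients by arm whose haemoglobin falls by at least 20 g/L from baseline to the on-treatment minimum, using scheduled and unscheduled values and irrespective of bleeding. The figure is already in the major-bleeding definition.
- Add the number and percentage by arm with on-treatment haemoglobin below 6 g/dL. The figure is already in exclusion criterion 4.
- Limit the denominator of each treatment-emergent row to patients not already in that category at baseline.

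Both figures serve only as descriptive reporting thresholds and change no clinical rule. The two new rows would also give the Protocol 8.5.4 commitment a haemoglobin criterion. They count falls from any cause, so they should be read as a comparison between arms.

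The cost is SAP wording and a few table rows, with no new data. Some patients will now be shown as worsened.
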